### **Target population and setting:**

Service User input: A sampling framework, using quota sampling based on sexual orientation, age and gender will be applied, including MSM and young heterosexuals aged  $\geq 16$  years old, to create four distinct groups in order to gain a broad range of opinions. Approximately 6-8 participants (n=24-32 in total) will be recruited to attend each focus group which will last 45 to 60 minutes. These groups are formed so that participants from our target communities with a high prevalence of STIs are able to share their thoughts and feelings freely amongst participants with similar experiences of sexual health provision. Eligible participants from our PPI group, in Brighton and in one London SH clinic (where researchers are based) will be invited to attend one of four focus groups being held at local community venues.

*Health Care Provider (HCP) input:* Four additional groups to will provide input from potential service providers (n=24-32). Two groups will be run with Sexual Health Advisors (one in Brighton and one in London) and two groups with HCP from GUM clinics or integrated contraception and sexual health services (again in Brighton and London).

**Data collection:** Discussions will be facilitated by two researchers trained in focus group methodology and will be transcribed verbatim by an external medical transcription service. Non-HCP participants will receive £20 as recompense in line with similar studies.

**Data Analysis** The transcripts will be analysed using a Framework Analysis approach (Ritchie and Spencer, 1994). This assists accurate reporting of individual experiences and opinions as well as the meanings attached to them, whilst maintaining predefined objectives (Pope et al, 2000). See WP3 for details.

*Outputs:* Manualised packages of interventions suitable for delivery in the context of existing sexual health services including clear guidelines on (1) which behavioural and self-regulatory needs and deficits each intervention is able to address and (2) what counts as faithful delivery in context including "must have" and must not have rules. Manualisation will be completed in WP6.

# Work Package 5:

*Objectives 7:* To determine the acceptability and feasibility of implementing the individualised package of interventions in different SH clinical settings,

*Objectives 8*: To assess the feasibility of testing this individualised package of behavioural interventions in a randomised controlled trial against usual care.

*Objectives 9*: To estimate the cost and resource implications of implementing the individualised intervention packages in different SH settings.

**Study Design**: It is envisaged that the best design for a definitive RCT would be cluster randomisation. We therefore propose to determine feasibility by conducting pilot implementations in a small number of clinics (n=6) representative of the range of sexual health services, without randomisation. Three further clinics will act as pilots for the control sites where patients will continue to receive standard of care, but consent to obtain follow-up outcome data will be sought. Outcomes will be assessed using a mix of qualitative and quantitative methods. As the collection of data used for triage is expected to be incorporated into routine care (data being collected routinely to meet the PHE requirements for behavioural surveillance) this data will be available for control and intervention sites.

Target population: Patients attending the pilot clinics and eligible for triage during a 6 month pilot period.

**Inclusion criteria:** Men and women, aged 16 and over, attending the pilot SH clinics with a new clinical episode

Exclusion criteria: Under 16, do not or are unable to consent

**Settings:** Nine clinics (6 intervention and 3 control pilot clinics) have been chosen as the minimum number to represent the range of sexual health clinical settings in the UK, within the constraints of resources (all have agreed in principle to participate). Clinics in and out of London have been included. All clinics will have access to at least a limited EPR facility, which is required to meet the PHE national surveillance requirements. Large London GUM clinic – The Mortimer Market Centre; high proportion of MSM; ethnically diverse Large non-London GUM clinic – The Royal Sussex County Hospital; high proportion of MSM. Medium-sized London GUM clinic - Archway Centre; large proportion ethnic minorities; small proportion of MSM

Medium-sized London GUM clinic - Kings College Hospital; ethnically diverse; small proportion MSM; fully integrated sexual health and contraception service.

Brook Advisory Service – three London clinics to be included (Euston, Southwark and Lambeth); primarily contraception services but provide level 2 sexual health services.

Small and medium-sized non-London GUM clinics - Swindon and Whittal Street, Birmingham.

**Interventions**: As developed in WP 4, it is expected that the package of interventions will include group delivered (e.g. waiting room videos), self-delivered (e.g. interactive digital interventions), clinician delivered (one-to-one motivational interviewing). Clinical staff will be trained on site by the research team in interpreting the triage results, and delivering the intervention.

**Recruitment and sampling:** Recruitment will take place in the 4 GUM clinics for 2 months and in the 2 Brook clinics for 3 months. All patients attending the clinic during the recruitment period will be provided with information that the clinic is piloting a new risk assessment tool which will help clinicians decide whether to offer interventions to reduce health risks associated with sexual behaviour. The information will make clear that, if they are advised to take part in a particular intervention, they can choose to accept the intervention, or not. All eligible patients attending the intervention and control clinics during the recruitment period will be asked by the clinician at the beginning of the consultation, prior to triage, whether or not they would consent to being approached after 3 months for telephone follow-up interview. If the risk assessment tool indicates a medium or high risk then the patient will be eligible to be offered an appropriate package of intervention(s). If the intervention via a website, on a computer in the clinic, and to access the intervention at home. If it is a face-to-face or telephone intervention they will be referred accordingly. The triage tool will be incorporated into the EPR systems of the participating clinics, so that all clinic attendees will be subject to this risk assessment and the result automatically recorded.

**Data collection and follow-up:** Once users are referred to a package of intervention their clinic ID will be their unique identifier. The unique identifier automatically generates a notification when a participant starts and finishes any part of the intervention (see figure 1). The proportions in the different steps of figure 1 will be extracted from the clinic EPR systems. A purposive sample of n=30 users who were offered the intervention but did not accept or dropped out at any point will be invited to participate in a semi-structured telephone interview exploring the reasons for not accepting the intervention or dropping out. A further n=30 semi-structured interview with HCP (clinicians and health advisors) will be conducted exploring their experience of the intervention.

A sample of the users who agree to telephone follow-up will be contacted by phone by a research nurse, three months after their appointment. The study aims and objectives will be explained and verbal consent for a telephone interview taken. The research nurse will conduct a brief telephone interview, collecting data on their experience of attending the clinic and the intervention (if they received it), sexual risk behaviour, whether or not they have been to an SH clinic and/or had an STI diagnosed since their clinic appointment and preferred mode of follow-up: e.g. clinic appointment or postal STI sampling kit. Based on their preferred choice of follow-up either a clinic appointment will be arranged or postal GC/CT sampling kit will be dispatched (figure 3)

In order to describe the impact of the intervention on the flow of users through the clinic and resource allocation clinic operations in the run up to the pilot, during the pilot and after the pilot will be observed. Based on the timings entered into the electronic patient records and aggregate clinic activity data to extract the following: Total time spent by service users in clinic, total number of service users seen, number of STIs diagnosed; average consultation time with clinician; and health advisors work load.

[figure not shown]

Figure 1: Flow chart for feasibility of the intervention with estimated proportions at each stage.

[figure not shown]

Figure 2: Flow chart for follow-up study

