## **Study outcomes:**

Acceptability of the intervention to users and HCP

- 1. Proportion of service users who attend the clinic that are scored by triage tool
- 2. Proportion of those who score high or medium who are offered the intervention
- 3. Proportion of those who are offered the intervention who take up the intervention
- 4. Proportion who take up the intervention who complete the intervention
- 6. Reasons for not completing the intervention from the qualitative study of participant

7. Acceptability of the intervention from the qualitative study of the staff

Feasibility and resource outcomes:

- 1. The total time spent by service users within the clinical service compared to normal
- 2. Total number of service users seen and STIs diagnosed, compared to normal
- 3. Average consultation time compared to normal
- 4. Number of patients seen by health advisors compared to normal
- 5. Extra HCP time required for the intervention
- Feasibility of active follow-up in an RCT
- 1. Proportion of service users who consented to the follow-up
- 2. Proportion of service users who were contactable at 3 months and complete the telephone interview
- 3. Proportion who had been for a STI screen or agreed to follow-up testing
- 4. Proportion of service users for whom there was a follow-up STI screen

**Data analysis/ sample size:** To investigate the feasibility of the intervention and understand the processes involved five measures will be collected: (i) the proportion of attendees triaged, among whom (ii) the proportion classified as medium or high risk, among whom (iii) the proportion offered the intervention, among whom (iv) the proportion that accept it, and among whom (v) the proportion who complete the intervention. All of these will be extracted from the EPR and calculated for each of the six centres implementing the intervention to see how this varies, and we will test for a difference in each between GUM clinics and Brook clinics by chi-squared test.

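### Four resource outcomes are compared with an undefined 'normal' and the control clinics are given no role in it, so calendar change and the consent request could be read as intervention effect

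*Protocol*

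**What the plan says.** Under Data collection and follow-up in Work Package 5, the protocol gives both a purpose and a method. The purpose is causal in wording: "In order to describe the impact of the intervention on the flow of users through the clinic and resource allocation". The method is that "clinic operations in the run up to the pilot, during the pilot and after the pilot will be observed", using timings in the electronic patient record (EPR) and aggregate activity data. The clinics to be observed are not named, and the windows before and after have no stated length.

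The Study outcomes section lists five feasibility and resource outcomes. Four have the same comparator:

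- "The total time spent by service users within the clinical service compared to normal"
- "Total number of service users seen and STIs diagnosed, compared to normal"
- "Average consultation time compared to normal"
- "Number of patients seen by health advisors compared to normal"

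The fifth, extra staff time for the intervention, has no such comparator. 'Normal' is not defined anywhere.

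On the controls, the Study Design paragraph says: "Three further clinics will act as pilots for the control sites where patients will continue to receive standard of care", with consent sought for follow-up data. The sample size section states an intervention-control comparison for the follow-up proportions and for nothing else.

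**The concern.** A change in a clinic between two periods combines the effect of the intervention with everything else that changed between them. Three candidates can be traced to the protocol.

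1. **Calendar change.** Recruitment lasts 2 months in the GUM clinics and 3 months in the Brook clinics, so adjacent windows of that length would fall in different parts of the year.
2. **The consent request.** Under Recruitment and sampling, clinicians at intervention and control clinics ask every eligible patient, at the start of the consultation and during recruitment, whether they may be contacted at 3 months. This is a burden of the study, not of the intervention, and it falls on consultation time.
3. **Routine behavioural data.** Collection is expected to be part of routine care at both kinds of site. If it began near the start of the pilot, it could also shift consultation time.

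At stake is the description of how the intervention affects flow and workload, which a later trial team and clinic managers would use. The acceptability and follow-up results do not depend on it.

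**Working it through.** The protocol states no effect size, standard deviation, precision or power for the resource outcomes, so there is no figure of its own to reproduce. What follows shows what a before-during-after comparison can and cannot remove.

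**Step 1: which disturbances cancel.** Compare the pilot window with before alone, with after alone, or with their mean, using equal adjacent windows.

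| Disturbance | Error against before | Error against after | Error against mean of both |
|---|---|---|---|
| Linear trend, slope b per window | b | −b | 0 |
| Lasting step of size d at pilot start | d | 0 | d/2 |
| Burden of size d in the pilot window only | d | d | d |

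The consent request belongs in the last row. If recruitment fills the observed window, neither outer period removes any of it. Subtracting the concurrent change at the control clinics does remove it, as far as the request takes equally long there. The protocol gives no duration. If it took 1 to 2 minutes of a 20-minute consultation (both assumed), the error would be 1/20 to 2/20, or 5% to 10%.

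**Step 2: seasonal change.** Assume an annual cycle of amplitude A and adjacent windows of m months. With h = πm/12, the average over a window centred at phase c is A·s·cos(c), where s = sin(h)/h. The worst-case errors are:

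- against the mean of before and after: A·s·(1 − cos 2h)
- against before alone: 2·A·s·sin(h)

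For m = 2: h = π/6, s = 0.955. The errors are 0.955 × 0.5 = 0.48A and 2 × 0.955 × 0.5 = 0.95A.

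For m = 3: h = π/4, s = 0.900. The errors are 0.900 × 1 = 0.90A and 2 × 0.900 × 0.707 = 1.27A.

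| Assumed A | 2 months, against mean | 3 months, against mean | 2 months, against before | 3 months, against before |
|---|---|---|---|---|
| 5% | 2.4% | 4.5% | 4.8% | 6.4% |
| 10% | 4.8% | 9.0% | 9.5% | 12.7% |

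These are maxima over all start dates. A pilot at another point of the cycle would have a smaller error.

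**Step 3: comparison with sampling noise, for patient counts only.** The sample size section expects 16,000 triaged patients. Assume Poisson counts, no overdispersion and equal windows. A comparison of two windows then has a 95% margin of 1.96 × √(2/16,000) = 2.2%. Against the mean of two outer windows the margin is 1.96 × √(1.5/16,000) = 1.9%. The seasonal errors against the mean run from slightly above that margin (2.4%) to several times it (9.0%). The check does not carry over to time in clinic or consultation time, for which no standard deviation is given.

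**Step 4: what the controls can offer.** The Settings list has six GUM and three Brook clinics. Recruitment and sampling refers to 4 GUM and 2 Brook clinics, which matches the six intervention sites. The controls are then apparently 2 GUM and 1 Brook, so the contrasts are 4 against 2 and 2 against 1. All nine clinics have at least limited EPR.

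**The case against.** The best defence is that the protocol promises only a description, in a non-randomised feasibility study, with no hypothesis or decision threshold on these outcomes, and that details of comparison can be left to an analysis plan. This stands as far as weight is concerned. It does not dispose of the point: which clinics to extract from, and for which dates, is a data-collection decision, and the protocol itself names the comparator and leaves it undefined.

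A reader might infer four stronger things that the documents do not support.

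- **That this is a simple before-during comparison.** It is not. An after period is planned, and averaging the outer periods cancels a linear trend. The error is something that could happen, not something that must.
- **That control clinics are excluded from the observation.** The text does not say which clinics are observed, so this rests on silence.
- **That routine behavioural data collection starts alongside the pilot.** The protocol speaks of "data being collected routinely to meet the PHE requirements for behavioural surveillance" and gives no start date for these clinics. Work Package 2 dates the dataset pilot from August 2013 in 10 clinics not identified as these nine. If collection was in place before the run-up, it does not bias the change.
- **That the cost per patient is distorted.** The Economic analysis records resources used to deliver the interventions and applies unit costs. It does not rely on the change from 'normal', and extra staff time has no such comparator either.

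A further objection concerns the remedy. The triage tool is to go into the EPR of the participating clinics, which leaves open whether control clinics run it. If they do, subtracting their change removes the triage burden, which belongs to the intervention. This is correct, and it is why the within-clinic change must be reported as well.

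**Conclusion.** The concern holds in a limited form. Four resource outcomes are compared with an undefined 'normal', and no section gives the control clinics a part in the comparison. Non-linear calendar change could be read as intervention effect, and so could the consent request made at both kinds of clinic during recruitment. A start of routine behavioural data collection near the pilot is a possible further source, but its date is not given.

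The size is illustrative. A worst-case seasonal error of 2.4% to 9.0% against the mean of before and after rests on an assumed amplitude of 5% to 10% and on equal adjacent windows of 2 or 3 months. The 5% to 10% for the consent request rests wholly on assumed durations. No figure in the protocol shows that a bias of either size will occur.

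The directly recorded extra staff time and the costing are unaffected. This is a cheap improvement, not a flaw that undermines the feasibility study.

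**What to change.** 1. Define 'normal' for the four outcomes by naming the clinics and the calendar windows before, during and after.
2. Extract the same aggregate EPR and activity measures at the three control clinics over the same windows.
3. Report descriptively, clinic by clinic, the within-clinic change and, beside it, the change in intervention clinics minus the change in control clinics.
4. State for each clinic when routine behavioural data collection began.
5. State whether the control clinics ran the triage tool. If they did, say that the contrast excludes the triage burden.

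The cost is a small extra extraction at three clinics already in the study. The contrast will be imprecise with six against three clinics, so it should carry no formal test. A single Brook control would give no between-clinic variance, so nothing beyond description is possible for Brook separately.

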## **Study outcomes:**

Acceptability of the intervention to users and HCP

- 1. Proportion of service users who attend the clinic that are scored by triage tool
- 2. Proportion of those who score high or medium who are offered the intervention
- 3. Proportion of those who are offered the intervention who take up the intervention
- 4. Proportion who take up the intervention who complete the intervention
- 6. Reasons for not completing the intervention from the qualitative study of participant

7. Acceptability of the intervention from the qualitative study of the staff

Feasibility and resource outcomes:

- 1. The total time spent by service users within the clinical service compared to normal
- 2. Total number of service users seen and STIs diagnosed, compared to normal
- 3. Average consultation time compared to normal
- 4. Number of patients seen by health advisors compared to normal
- 5. Extra HCP time required for the intervention
- Feasibility of active follow-up in an RCT
- 1. Proportion of service users who consented to the follow-up
- 2. Proportion of service users who were contactable at 3 months and complete the telephone interview
- 3. Proportion who had been for a STI screen or agreed to follow-up testing
- 4. Proportion of service users for whom there was a follow-up STI screen

**Data analysis/ sample size:** To investigate the feasibility of the intervention and understand the processes involved five measures will be collected: (i) the proportion of attendees triaged, among whom (ii) the proportion classified as medium or high risk, among whom (iii) the proportion offered the intervention, among whom (iv) the proportion that accept it, and among whom (v) the proportion who complete the intervention. All of these will be extracted from the EPR and calculated for each of the six centres implementing the intervention to see how this varies, and we will test for a difference in each between GUM clinics and Brook clinics by chi-squared test.

The sample size is estimated from proportion (v) as this uses the smallest denominator. It also determines the number of participants who experienced the intervention. A total of 16000 patients attending the trial sites during the feasibility study period will be triaged leading to at least 400 completing the intervention (see figure 1), from among at least 800 accepting it, based on the above estimates. This sample size allows proportion (v) to be estimated with expected 95% confidence interval of 46 to 54%, and assuming 200 accept the intervention in Brook clinics and 600 at GUM. This provides over 80% power to detect a difference in completion such as 44 vs. 56% between these clinic types.

To investigate the feasibility of collecting the follow-up data envisaged for the main trial we will ask attendees whether they will agree to telephone follow-up. We will then, in a subsample of 400 from implementation site clinics and 300 from the control clinics, conduct telephone follow-up and calculate (i) the proportions opting for either a return visit to the clinic, or to be sent a kit for home sampling, and (ii) from among the two groups calculate the proportion completing follow-up (i.e. returning to clinic or returning a kit for testing). We will compare these proportions between GUM and Brook, and between clinics implementing the intervention and control, and between groups opting for a clinic appointment or home sampling. Analysis will use chi-squared test and logistic regression, to examine these differences jointly.

This sample size, if the overall follow-up is assumed to be around 60%, gives a 95% confidence interval of 56 to 64%. Assuming at least 150 select each follow-up method at intervention clinics and 120 at control clinics then we will have over 80% power to detect a difference of 53 vs. 67% in completed follow-up, and a difference of 54 vs. 66% between intervention and control clinics. Qualitative data will be analysed as in WP3

**Economic analysis:** An assessment will be made of the (incremental) costs of delivering the package of interventions, by recording the resources, such as staff time, that are required to deliver the interventions during the feasibility study and by applying appropriate NHS unit costs. Interviews with health care professionals, service manages and commissioners will be undertaken if necessary to supplement the data collection exercise. The overall output would be an estimate of the per-patient cost of delivering the intervention and the cost that would be required to fund the intervention in a fully powered RCT. The intention would be to perform a full economic evaluation if a full RCT of the intervention is later commissioned.

## Work Package 6

*Objective 10*: To refine the manual of the intervention package and to outline a feasible trial design (if feasibility is supported).

**Manual development**: Complete specification of the intervention package(s), standard operating procedures, and potential staff and cost implications will be developed for the different intervention packages in different setting. An associated training tool and post-training assessment for clinicians and health advisors will be developed, informed by the training of clinical staff during the trial. The manual and the training are expected to be interactive, web based components with the potential for refresher training to be added in.

**Design of a proposed RCT**: This is likely to comprise a cluster randomised control trial with a combination of active follow-up, supplemented by routinely collected clinical and surveillance data. Feasibility challenges will be reported. If a trial is deemed unfeasible, alternative evaluation methods will be proposed.

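### Work Package 5 tests and powers two comparisons between groups of clinics (4 vs 2 and 6 vs 3) as if patients were independent, so the stated power holds only if clinics hardly differ

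*Protocol*

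**What the plan says.** All of this is in the protocol, Work Package 5.

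- **Design.** The pilot is not randomised. "Nine clinics (6 intervention and 3 control pilot clinics) have been chosen as the minimum number to represent the range of sexual health clinical settings". For the intervention clinics, "Recruitment will take place in the 4 GUM clinics for 2 months and in the 2 Brook clinics for 3 months". The protocol also holds that "the best design for a definitive RCT would be cluster randomisation".
- **Process measures** (Data analysis/ sample size). Five proportions, from triage to completion, are tabulated for each of the six implementing centres to show how they vary. Then "we will test for a difference in each between GUM clinics and Brook clinics by chi-squared test".
- **Precision and power for completion.** "This sample size allows proportion (v) to be estimated with expected 95% confidence interval of 46 to 54" per cent, with 400 completing "from among at least 800 accepting it, based on the above estimates". The acceptors are split 200 Brook and 600 GUM. "This provides over 80% power to detect a difference in completion such as 44 vs. 56% between these clinic types".
- **Follow-up.** A subsample of 400 intervention and 300 control patients is compared by clinic type, by intervention vs control, and by chosen follow-up method, using chi-squared tests and logistic regression. The interval for 60% follow-up is given as 56 to 64%. Assuming at least 150 patients per method at intervention clinics and 120 at control clinics, power above 80% is claimed for 53 vs 67% and for "a difference of 54 vs. 66% between intervention and control clinics".

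No ICC, design effect, clinic effect or robust variance appears with any of these tests, intervals or power figures.

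**The concern.** GUM or Brook, and intervention or control, are attributes of a clinic. No patient within a clinic differs from another on either. The information about these contrasts therefore comes from six clinics in one case and nine in the other, however many patients each contributes. A patient-level chi-squared test counts ordinary differences between clinics as evidence about clinic type or about the intervention. Its type I error then exceeds the nominal level, and a power figure based on patient counts is too high.

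The protocol gives its own reasons to expect clinics to differ. It selects them to span size, location and patient mix, it tabulates the proportions by centre, and it expects a cluster-randomised main trial. The results are meant to inform that trial's design, so a clinic-type or arm difference that is only clinic-to-clinic noise could mislead. The between-clinic variance, which a cluster design needs, is not among the planned outputs.

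**Working it through.** **Inputs from the protocol.** Completion: 600 GUM acceptors in 4 clinics (m = 150 per clinic) and 200 Brook acceptors in 2 clinics (m = 100), 44 vs 56%. Follow-up: 2 × 150 = 300 patients in 6 intervention clinics (m = 50) and 2 × 120 = 240 in 3 control clinics (m = 80), 54 vs 66%.

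**Assumptions.** Two-sided alpha of 5% (none is stated), equal clinic sizes within each group, and ICC ρ from 0.001 to 0.05 (none is given). Around 50%, the between-clinic SD is √(0.25ρ): about 1.6, 3.5, 5 and 11 percentage points at ρ = 0.001, 0.005, 0.01 and 0.05.

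**Step 1: reproduce the stated figures with independent patients.**
- Completion interval: 0.50 ± 1.96√(0.25/800) = 46.5 to 53.5%, which is 46 to 54% rounded outward.
- Follow-up interval: 0.60 ± 1.96√(0.24/700) = 56.4 to 63.6%, which rounds to 56 to 64%.
- GUM vs Brook: SE = √(0.2464/600 + 0.2464/200) = 0.0405; 0.12/0.0405 = 2.96; power = Φ(2.96 − 1.96) = 84%.
- Intervention vs control, 300 vs 240: SE = √(0.2484/300 + 0.2244/240) = 0.0420; 0.12/0.0420 = 2.86; power = 82% (81% if the two percentages are swapped). With 400 vs 300 it is 90%.

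The figures contain no allowance for clustering.

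**Step 2: add clustering.** For each group, d = 1 + (m − 1)ρ and variance = p(1 − p)d/n. The type I error of the plain chi-squared test is 2Φ(−1.96/√R), with R = (d₁/n₁ + d₂/n₂)/(1/n₁ + 1/n₂).

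At ρ = 0.01:
- GUM vs Brook: d = 2.49 and 1.99; SE = √[0.2464(2.49/600 + 1.99/200)] = 0.0589; 0.12/0.0589 = 2.04; power = Φ(0.08) = 53%. R = 2.115, type I error 18%.
- Intervention vs control: d = 1.49 and 1.79; SE = √(0.2484 × 1.49/300 + 0.2244 × 1.79/240) = 0.0539; 0.12/0.0539 = 2.23; power = Φ(0.27) = 60%. R = 1.657, type I error 13%.

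The t columns use the same SE with a noncentral t on clinics − 2 degrees of freedom. They are separate because having few clinics costs power even when ρ = 0.

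| ICC | GUM vs Brook: power, normal | power, t (4 df) | type I error | Intervention vs control: power, normal | power, t (7 df) | type I error |
|---|---|---|---|---|---|---|
| 0 | 84% | 61% | 5% | 82% | 69% | 5% |
| 0.001 | 80% | 57% | 6% | 79% | 66% | 6% |
| 0.005 | 66% | 44% | 12% | 70% | 57% | 9% |
| 0.01 | 53% | 35% | 18% | 60% | 48% | 13% |
| 0.05 | 21% | 15% | 44% | 28% | 23% | 34% |

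A beta-binomial simulation of the GUM vs Brook test gave type I errors of 12, 18 and 46% at ICC 0.005, 0.01 and 0.05, in line with the formula.

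**Step 3: tipping points.** With the normal reference, power falls below 80% at an ICC of about 0.001 for GUM vs Brook. For intervention vs control the value is about 0.0004 to 0.0006 on 300 vs 240, and about 0.004 on 400 vs 300.

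**Step 4: more patients per clinic do not cure it.** As m grows with 4 and 2 clinics, the SE cannot fall below √[0.2464ρ(1/4 + 1/2)]. At ρ = 0.02 this is 0.0608, so power for 44 vs 56% cannot exceed Φ(0.12/0.0608 − 1.96), about 51%. For the same reason, type I error is worse for the process measures with larger denominators. For the proportion triaged, taking 16,000 patients and assuming a 3:1 GUM:Brook split, it is about 58% at ICC 0.005.

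**Step 5: intervals.** The size-weighted m is (4 × 150² + 2 × 100²)/800 = 137.5 for completion and (6 × 66.7² + 3 × 100²)/700 = 81 for follow-up. With normal limits:

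| ICC | Completion | Follow-up |
|---|---|---|
| 0.005 | 45.5 to 54.5% | 55.7 to 64.3% |
| 0.01 | 44.7 to 55.3% | 55.1 to 64.9% |

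**The case against.** **The loss depends on an ICC that the protocol does not give.** This stands as a limit on the size. The tipping points are very low, however: an ICC of 0.001 is a between-clinic SD of about 1.6 points, among clinics chosen to differ.

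**Inference could be confined to these named, purposively chosen clinics.** For the two intervals this is a fair defence, and at ICC 0.005 they barely move. It does not rescue the comparisons, which are framed as differences between clinic types and between intervention and control.

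**This is a feasibility pilot, and centre-specific process proportions will be reported anyway.** That lets a reader see the variation and lowers the severity. It does not make the power claims or the tests correct.

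**Deferral to a statistical analysis plan.** This does not help, because the protocol itself names the test and states the power.

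Stronger readings that a reader might infer, and that the protocol does not support:
- *All three power claims fail.* The 53 vs 67% claim compares clinic appointment with home sampling. Patients choose between these largely within a clinic, so the argument does not carry over.
- *Every GUM vs Brook test rests on 4 vs 2 clinics.* That count holds for the process measures. The follow-up comparison by clinic type may draw on all nine clinics.
- *A false difference would pass straight into the main trial.* No decision rule is tied to these tests. Work Package 6 says only that a cluster trial is likely and that feasibility challenges will be reported.

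**Conclusion.** The point holds for the chi-squared tests of GUM vs Brook and of intervention vs control, and for the two power claims attached to them. Their arithmetic is right only for independent patients. Over assumed ICCs of 0.005 to 0.01, power with a normal reference is 66 to 53% for completion by clinic type and 70 to 60% for follow-up by arm. A t reference lowers this to 44 to 35% and 57 to 48%. Type I error is 12 to 18% and 9 to 13%. These sizes rest on the assumed ICC, equal clinic sizes within each group, and a two-sided 5% level.

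The intervals are a secondary matter. They are acceptable as statements about the participating clinics, but not as statements about such clinics in general.

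This should be fixed but is not critical: the study is a non-randomised feasibility pilot with no go/no-go rule resting on these tests.

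**What to change.** In Work Package 5, Data analysis/ sample size:

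1. Delete the power claims for 44 vs 56% completion and 54 vs 66% follow-up, or restate them over a stated ICC range with the number of clinics on each side.
2. For GUM vs Brook and intervention vs control, replace the patient-level chi-squared tests. Either present clinic-specific proportions descriptively, or compare clinic-level summaries (t with 4 and 7 df for the 4 vs 2 and 6 vs 3 contrasts), or fit a random-clinic logistic model with a small-sample correction. Treat the joint logistic regression of follow-up in the same way.
3. Label the 46 to 54% and 56 to 64% intervals as applying to the participating clinics only, or widen them for clustering.
4. Add the estimated between-clinic variance, with its uncertainty, as an output for the trial design in Work Package 6.

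The cost is protocol wording, slightly more analysis, and less favourable stated power and precision. No extra patients are needed.
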